## Project summary

WeReha is an innovative device for the home rehabilitation of stroke patients developed within the scope of the EU funded project MAGIC-PCP [5]. WeReha is a system that allows patients to perform exercises in a home environment with remote supervision integrated within regular rehabilitation. The principle on which the product is based is that of biofeedback guided rehabilitation, designed to stimulate muscle recovery and contribute to a more effective and more motivating rehabilitation of neuro-motor patterns. WeReha is completely adaptable, allowing only authorized to assign exercises, by planning specific sequences of movements.

WeReha product is composed by the following elements:

- a tablet with a proprietary application on it (the “WeReha app”)
- an inertial sensor with accelerometers, gyroscopes and magnetometers (the “sensor”)
- elastic straps allowing the user to wear it on different parts of the body (the “straps”)
- a series of 3D printed objects where the sensor can be placed that become animated (the “smart objects”)
- a web portal for clinical staff through which they can manage and monitor users (the “web-application”)

The WeReha app presents the patient with a series of rehabilitation exercises in the form of a number of interactive games, driven by body movement, which is captured by the sensor or the hand specific movements using the smart objects. A session with WeReha always starts with a questionnaire on the system, through which the software gains an understanding of the patient's health conditions and the presence or not of a caregiver for the session. Based on this questionnaire, the software adapts the daily session to minimise risks while maintaining a high level of rehabilitation to help the patient reach their goals. The device works with and without an internet connection, but when the device is connected to the internet, supervisors are able to provide supervision and remote support through a web application.

The web application is hosted on a dedicated server located inside the hospital. Only trained staff will be provided with access to the web application with a unique username and password required for sign on. The exercises assigned for the client to perform at home, are at the discretion of the clinician who is caring for the patient and might require the presence of a caregiver.

The goal of this study is to investigate the applicability and utility of an innovative technology product such as WeReha to the home rehabilitation of stroke patients as an integrative solution to

a conventional exercise program and to assess its acceptance by the patient, caregivers and clinic professionals.

Patients will use WeReha for their home rehabilitation in addition to traditional treatments for up to 12 weeks. The Inclusion criteria for the study have been kept broad in order to assess these factors on a large enough scale, so as not to limit the usage of the device to a specific sub-group of patients. If patients enrolled are in a subacute phase (i.e. within the first 6 months after the stroke onset), they will be enrolled before leaving the hospital or the rehabilitation department and reaching their home. If patients are considered to be in their chronic phase (i.e. over 6 months after stroke onset), they will be enrolled during an outpatient treatment or on a volunteer basis.

Before starting the trial with WeReha, every patient enrolled will receive proper training from a person dedicated to the project (who will be referred to as the “dedicated figure”) appointed by the hospital and financially supported by the sponsor of the study.

## Rationale & background information

Stroke is one of the largest causes of adult disability in the world. Every year it is estimated that approximately 15 million people worldwide suffer a stroke; of these, 5 million die and another 5 million are left permanently disabled, placing a burden on families and communities. Around 20% of stroke survivors are under the age of 65 and hence are still a productive working age [1].

Rehabilitation is one of the most important aspects of care for patients following a stroke and is proven to affect the eventual level of recovery and independence achieved. Community stroke services that provide rehabilitation exist in the study region, and are able to provide support, lifestyle advice and risk factor assessment. Charitable organisation often provides a range of valued support services for stroke patients and their caregivers in the community. When patients leave the hospital quickly after stroke to receive intensive rehabilitation in their home environment it is called ‘Early Supported Discharge’ (ESD). This is usually for people who have milder disabilities after stroke and are able to move about unaided or with minimal help.

There is evidence to suggest the quality of care and outcomes for patients who have sustained a stroke may be improved by an increase in the amount of therapy patients receive. Very often, additional therapy is warranted and needed after 12 weeks and after the standard six month review. It is difficult for patients to access additional therapy services mostly due to cost. Community Stroke services are not widely available nor is it affordable to provide the services needed for many patients. Additionally, the staff needed to provide the services needed, are unavailable and unsustainable [3]. For example, UK service standards indicate that patients referred to community stroke teams should be reviewed between one and three days after hospital discharge. However, the 2015 Post- acute Stroke National Audit found that patients in Northern Ireland may wait up to 5 days after discharge before contact is made by a community stroke team. The rising cost of care, rehabilitation and fiscal constraint create a real risk of a continuing shortfall in therapy provision, thus failing to optimise personal independence for stroke patients. If personal independence is not optimised for stroke patients there is both a detriment to the individual and to society through the economic cost of providing long-term care and support. As a consequence, a project such as WeReha is of critical importance to the healthcare system and the economic implications of the current trend. Testing alternative cost effective methods of optimising recovery and Human Resources are of utmost urgency.

It is widely accepted that timely access to rehabilitation is a key factor in the recovery for people who have survived a stroke. Therapy-based rehabilitation appears to improve independence in personal activities of daily living according to evidence based guidelines [4]. The use of self-management approaches to help patients and caregivers better manage the life-changing impacts of stroke presents an opportunity to improve patient care in a cost effective way [9]. WeReha has been developed to be a cost-effective and accessible system for the greatest possible number of service providers and patients. We recognize that an innovative use of technology may enable providers of stroke services to realistically meet the growing demographic demands on their services and facilitate acceptable or improved care outcomes for stroke patients in Europe.

For these reasons, there is significant benefit in using a solution such as WeReha to enhance the cost-effective provision of rehabilitation for this patient population.

By applying innovative ideas and re-engineering care delivery systems with new solutions such as WeReha, it becomes possible to consider real technological solutions for stroke rehabilitation and the improvement of the well-being of these patients across Europe. WeReha, within the scope of the Magic project [5] seeks to achieve this specifically by optimising the recovery of physical function and personal independence in order to reduce the overall socioeconomic burden of this disease.

Many stroke survivors suffer postural and balance problems, in addition to hand motor problems as well as other physical challenges. Decreased mobility limits daily life activities and therefore should be a focus for society by increasing movement leading to overall improvement. Virtual reality and biofeedback balance training has already been used in stroke rehabilitation, and previous studies have shown that such technology could improve balance ability ([13, 28]). The

mechanism we want to use even in WeReha is multi-sensory feedback with repeated practices that could facilitate motor learning and brain neuroplasticity.

Compared to conventional rehabilitation, WeReha could also increase subjects' motivation and satisfaction. It is the goal of this study to assess at scale the possible impact of a technology such as WeReha.

A study conducted by the Magic PCP buyers group [5] revealed several important factors for stroke survivors and their caregivers. Stroke patients emphasised that the needs of stroke survivors are not static - they evolve over time - and thus any potential solution should be designed to take this into account. In addition, consultation with a range of stakeholders (clinicians, therapists, patients, families and caregivers) about potential innovative solutions that might improve physical function and personal independence, in the first six months of stroke onset and long term thereafter, highlighted a technology that could provide a range of adjunct solutions to the care process.

Several studies have been conducted where a technology is involved for the care of stroke survivors. Most of them, including control groups, rated the experience as more pleasurable, enjoyable and beneficial ([28], [14]) than the conventional therapy, making the patient more motivated to train.

Türkbey and Kutlay [14] reported a treatment attendance ratio for total training time and training time/session equal to 87% and 90%, respectively; Wittman et al [15] reported that the weekly training did not change over the course of the intervention. Furthermore this positive approach to the technology seems to stimulate a greater daily motor activity (i.e. steps/day) beyond the training sessions [24], [26] with a great gain in quality of life. In addition, the literature reports significant evidence of improvements in functional abilities of stroke patients after a training period with technological devices ([9], [13], [14], [15], [23], [24], [25], [26], [27] [28], [29], [30]). There are also several studies and trials investigating the use of technology in a home environments for stroke survivors to treat upper extremities ([17], [18], [21]) in general for tele-rehabilitation services ([16], [20]) or cognitive treatments [22], but results have been either not presented or shown to be not significant.

Considering the results already obtained in evaluating the clinical efficacy of a technology applied to home-rehabilitation of stroke patients, our clinical trial is primarily designed to analyse the effects of WeReha on a sample of stroke patients, in terms of validity and acceptance by patients, professionals and caregivers.

Though the usage of a technology to improve home rehabilitation is generally assumed to be a factor for improvement in hospitals and community both economically and logistically, no large scale studies have been conducted, so far, to analyse the impact of technology in the process of stroke rehabilitation. Through this study we aim to evaluate the impact of our technology with outcomes dedicated to assess patient's involvement, acceptance, satisfaction and improvement.

## Study goals and objectives

The goal of this study is to assess the acceptance and validity of a new technology such as WeReha for home rehabilitation of patients following a stroke episode either in sub-acute or chronic phase. The investigation will be conducted in two different countries: two sites in Northern Ireland and one in Italy.

This study is part of the EU funded Magic PCP project [5], where three different companies will perform similar types of study. Every company will be assigned from September 2018 a trust in Northern Ireland and a site in Italy from among the following: Hospital Le Torrette, Ancona, University D'Annunzio, Chieti, ASL3 Pinerolo, Torino. Once a company has received approval for funds to perform the study (before September 2018), it will also be assigned the site in Italy and then it will apply for the Ethical Committee of that site. Every company is also required by the Magic PCP project [5] to provide 75 devices per country (150 in total). From now on, we will refer to the number of patients relevant to the Northern Irish site..

Let us define the terms and list assumptions we will use throughout the protocol:

- “enrolled patient”: a patient is considered enrolled in the study if they are within the inclusion criteria and voluntarily accept to participate and sign the consent form
- “active week”: a week in which the patient has performed at least three sessions with WeReha for a minimum of 15 minutes each (as measured by the software)
- “active patient”: a patient that has used the device for at least 4 “active weeks”
- “maximum time frame of usage”: 20 weeks, according to patients and clinicians feedback collected during our feasibility study (see [Safety Consideration](#) section)
- “end of usage”: if the participant does not have four active weeks in the first eight weeks of usage or the patient has reached the “maximum time frame of usage” or the patient has voluntarily decided to interrupt the study (drop-off)

The study aims to evaluate as a primary outcome quantifiable measure, the acceptance of technology, through analysis of the following:

- number of enrolled patients at the end of the trial period will be evaluated in order to understand the degree of acceptance of a technology such as WeReha, with the minimum target of 50 patients.
- number of “active weeks” with the device among the patients enrolled
- average minutes of exercise per day conducted with the technology as an objective measure for activity participation
- acceptance of technology, based on the Technology Acceptance Model / TAM as in [11] and [33] provided to patients at the end of the study (see [Annex B](#)).

All previous measures will be evaluated in general and for 6 different age-gender groups (male and female below 55, between 55 and 70, above 70).

As secondary outcome measures we will assess objective scales and scores typical for stroke rehabilitation:

- the Barthel index (see [10], [19], [6], [8])
- the Modified Rankin Score (see [19], [30], [7], [8])
- 

These scores will be compared with standard values and the goal is to show equivalency or improvement from those standard values after the treatment with WeReha.

In addition, we want to demonstrate the logistical and economic benefits of the deployed solution. Dedicated figures (a nurse or physiotherapist hired to run the Clinical Trial research study as explained in the Methodology section) will objectively measure the time taken to training patients and caregivers before leaving the trial site with the device and the number of times patients contact the sponsor for technical assistance.

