#### **Primary Outcome Measures:**

- Total number of patients enrolled -> KPI: minimum 50 patients enrolled;
- Total number of active patients -> KPI: minimum 40 active patients;
- Total number of patients who drop off, meaning that started the study and had less than 4 active weeks
- Average number of active weeks for each patient: the average number of active weeks is evaluated as the total number of active weeks divided by the number of patients enrolled -> KPI: 8 weeks (excluding drop off before 4 weeks)
- Activity participation, measured in average minutes per day dedicated to exercises with WeReha (measured during active weeks only) -> KPI: min. 45'/week
- Acceptance of the rehabilitation platform WeReha by the patient, evaluated through a questionnaire completed at the end of the study by every participant who consents to the study (see attachment ... )
- Previous results will be analysed on different age/gender groups. Age groups are: <55, 55-70, 70-85 both for male and female, for a total of six groups. Target would be to enroll patients within these groups as homogeneously as possible, but since we cannot foresee patients distribution there are no KPIs set for this outcome

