#### **Secondary Outcome Measures:**

- Barthel index and Modified Rankin Score: change from baseline (measured when receiving the device) at the end of the rehabilitation treatment (when returning the device)
- Time dedicated by the specialised personnel to each patient for training to learn the WeReha device before leaving the trial site (measured in minutes/patient)
- Number of calls per week for clinical and technical assistance specific for the WeReha device, registered on a paper or software spreadsheet by the sponsor

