- ii)     ii) how to position the sensor inside it,
- iii)     iii) how to move the object in order to reach the game’s target.

Once the sensor is worn or positioned inside an object, before starting the game, the patient is guided through a calibration phase to measure the sensors initial orientation in the space which acts as a reference position for all the movements recorded during the game. This process not only makes the measures more accurate but also nullifies any sensor wrongly positioned when worn (i.e. sensor overturning, rotations, inclinations respect to the body frontal plane).

In this pilot study investigators will recruit as many patients as possible as defined within the inclusion and exclusion criteria. There will be 75 devices available at the site from September 2018 to December 2019. Each patient will be provided with a WeReha device including the tablet and its charger, the inertial sensor and its charging station and cable, a kit of elastic straps together with a Velcro pocket and the 3 plastic objects. Every device can be used twice in order to assess as many patients as possible, providing a new set of straps and smart objects (that are to be considered single user only) and cleaning the other components by following specific and simple instructions provided by CoRehab.

Participants will be consented following a diagnosis of stroke and will keep the device for a maximum of 20 weeks following discharge from the hospital setting. This amount of time has been decided following review by clinicians and therapists during our earlier feasibility work. After that the tablet and the sensor will be collected, cleaned to ensure no cross contamination and meeting infection control guidelines within each Trust and made available for further use... The elastic straps with the pockets and the smart objects are the only personal and single use components, which will be disposed of after use... Secondary outcomes will only be assessed on “active patients”.

There will be a WeReha server available as a cloud solution, compliant with NCSC Cloud Security Principles, on which the web application will run and all the data will be collected whenever a patient’s device is connected to the internet. It is important to highlight that internet connection is not mandatory for the device to work properly as it will propose exercises to the patient as they were prepared initially after patient’s discharge. Then, whenever the device is

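### The 8-week usage KPI divides by all enrolled patients yet excludes early drop-offs, so the same data can meet or miss it; separately, the Barthel and Rankin changes are selected on device use

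*Combined protocol and SAP*

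**What the plan says.** **The KPI.** The combined protocol and SAP lists the average number of active weeks per patient among its Primary Outcome Measures. It is calculated as "the total number of active weeks divided by the number of patients enrolled", and its target is "KPI: 8 weeks (excluding drop off before 4 weeks". Study goals and objectives describes the same measure as active weeks "with the device among the patients enrolled". A patient counts as enrolled on eligibility, acceptance and signed consent; use of the device plays no part.

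**The label.** The bullet directly above the KPI counts "Total number of patients who drop off, meaning that started the study and had less than 4 active weeks", with no reason required. The definitions list in Study goals and objectives opens with "Let us define the terms and list assumptions we will use throughout the protocol". There, under the end of usage, the label sits on one route only: "or the patient has voluntarily decided to interrupt the study (drop-off". Low use in the first eight weeks is listed as a different route.

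**The decision rule.** Data Management and Statistical Analysis plans no statistical analysis of the primary outcomes and treats them as good when the KPIs are reached.

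**The functional scales.** Secondary Outcome Measures takes the Barthel and Rankin change from baseline "at the end of the rehabilitation treatment (when returning the device". Study Design sets the population: "Secondary outcomes will only be assessed on" active patients, meaning those with at least 4 active weeks.

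**The concern.** The KPI line gives two incompatible instructions. Dividing by everyone enrolled keeps patients with little or no use in the denominator; excluding early drop-offs takes them out. The line does not say whether the excluded patients leave the numerator, the denominator or both, or whether its 4 weeks are calendar or active weeks. With no test or interval beside the KPI, whoever runs the analysis would choose the denominator after seeing the data, and that choice could settle whether the target was reached.

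The second issue is separate. The plan wants to show equivalence with, or improvement on, standard values for Barthel and Rankin. If only patients who used the device for at least 4 active weeks are scored, the pre/post change describes a group selected on use. A reader cannot tell how the remaining patients fared on the same scales.

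**Working it through.** The 8 weeks is a target, not a derived figure, so there is no calculation in the plan to reproduce. The check asks what each reading gives on one set of data.

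**Inputs from Primary Outcome Measures:** at least 50 enrolled, at least 40 active, target 8 weeks.

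**Assumptions, not in the documents:** active patients average exactly 8 weeks; each of the others has w active weeks, with w from 0 to 3.

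**Step 1. Patients affected.** 50 − 40 = 10, or 20% of those enrolled. Active patients contribute 40 × 8 = 320 active weeks.

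**Step 2. The average under each reading.**

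| Reading | Formula | Average | Target met? |
|---|---|---|---|
| Active patients only | 320/40 | 8.00 | yes |
| All enrolled, all weeks counted | (320 + 10w)/50 | 6.40 to 7.00 | no |
| Low users' weeks removed, all enrolled in the denominator | 320/50 | 6.40 | no |
| Only voluntary stoppers excluded, 5 of the 10 kept in | (320 + 5w)/45 | 7.11 to 7.44 | no |
| Only voluntary stoppers excluded, 2 of the 10 kept in | (320 + 2w)/42 | 7.62 to 7.76 | no |

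With better retention, 45 active of 50 and the 5 others kept in, the average is 360/50 = 7.20 to 375/50 = 7.50.

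**Step 3. When the verdicts differ.** If m low users stay in, the active-patient mean a must satisfy (40a + mw)/(40 + m) ≥ 8, so a ≥ 8 + m(8 − w)/40.

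- m = 10: 8 + 10 × 5/40 = 9.25 (w = 3) to 8 + 10 × 8/40 = 10.00 (w = 0)
- m = 5: 8.625 to 9.00
- m = 2: 8.25 to 8.40

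Below an active-patient mean of 8.00 every reading misses. At or above the limit shown, both readings pass. Only between the two does the choice decide.

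**Step 4. What the two uses of the label add.** A patient who stops by choice after 6 active weeks is a drop-off in the definitions list but not in the outcome list. A low user whose device is taken back at the eight-week review is the reverse. A patient who consents and never starts is enrolled, but is not a drop-off under the outcome list, which requires having started. Aligning the label would therefore still leave the word enrolled in the formula.

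**Step 5. The functional scales.** At the minima, let A be the mean change in the 40 active patients and E that in the other 10. The mean over all 50 is 0.8A + 0.2E, so the active-only mean differs from it by 0.2(A − E). The documents give no value for the gap A − E. Assumed gaps of 5, 10 and 20 Barthel points would shift the mean by 1, 2 and 4 points.

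**The case against.** The strongest reply is that the intended meaning is not hard to find. The outcome list defines drop-off in the bullet just above the KPI, and the phrase in the KPI line is probably a loose restatement of it. On that reading the denominator is the active patients. In the definitions list the term being defined is the end of usage, and the label is only a parenthesis. This largely stands. A reader might infer that the two meanings of drop-off are what break the KPI; the documents do not support that, because the clash between enrolled and excluding lies within the KPI line itself. What the reply does not remove is that the written formula still names enrolled patients, as does Study goals and objectives.

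It is also fair to say that the different verdicts arise only within a window, and that enrolled, active and drop-off counts are reported separately, so poor retention would be visible. Both points limit the size of the problem. Neither tells the analyst which average to hold against the target.

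On the functional scales, a reader might infer that loss of function in anyone stopped early, including for harm, cannot appear in the results. The documents do not support that. An active patient is defined by at least 4 active weeks, whatever ended the use, so someone stopped early after reaching that number is still scored. Safety Considerations records adverse events for every participant from consent to the last visit, and persistent or significant disability is a serious event. A reader might also infer that the plan promises end scores for each patient and then contradicts itself. Secondary Outcome Measures and the data-collection text in Study Design give only the timing; it is the export description in Annex A that speaks of each patient. Restricting the analysis to active patients is an explicit choice in a pilot. The remaining point is that the result is selected on use and nothing is shown beside it.

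**Conclusion.** The concern holds in a limited form. The 8-week KPI contradicts itself within its own line, and because the primary outcome is judged on KPIs alone, this can change the verdict. At the plan's minima the same data give 8.00 (met) over active patients or 6.40 to 7.00 (missed) over all enrolled. That rests on an assumed active-patient mean of exactly 8 weeks and 0 to 3 active weeks in each of the other 10. More generally, the two readings disagree when the active-patient mean is at least 8.00 and below 9.25 to 10.00, and over a narrower range if only some low users are kept in. The documents give no expected number of low users, so how likely this is cannot be stated. The looser use of the label for voluntary stopping is a contributing ambiguity.

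Separately, the Barthel and Rankin change is conditional on at least 4 active weeks and should be described that way. At the minima it leaves out 20% of enrolled patients. The resulting shift depends on a gap for which the documents offer no figure.

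**What to change.** 1. **Primary Outcome Measures.** State that the 8-week KPI is the total of active weeks in active patients divided by the number of active patients. Report beside it the average over all enrolled patients, counting those who never started as 0.
2. **Study goals and objectives.** Reserve drop-off for fewer than 4 active weeks and call the patient's own decision to stop voluntary withdrawal. Record the reason for ending for every patient who ends before 20 weeks, including those with 4 or more active weeks.
3. **Study Design.** Keep the active-patient analysis of Barthel and Rankin. Also report, separately and with the week of measurement, the scores of patients with fewer than 4 active weeks who are scored when they return the device. Because they are measured earlier, they should not be pooled with the active group.

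The cost is a few sentences, one reason-for-ending field (the anonymised export described in Annex A lists none) and a short extra assessment at early device return. That assessment is added work: Methodology places final assessments after 20 weeks and mentions only device return at the eight-week review. Some withdrawn patients may decline it, and the added results lines may hold few patients.

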## Data Management and Statistical Analysis

As the primary outcomes of the study are designed to evaluate the impact and acceptance of a new rehabilitative technology for stroke patients, a statistical analysis on the primary outcomes will not be conducted. On the other hand, the study clearly aims to evaluate the number of patients, meeting the inclusion/exclusion criteria that are willing to use this technology and the time they will be using the devices at home. It has also to be noted that this study is part of a research project (Magic-PCP, [5]) where 3 companies will provide their solutions to 1 hospital in Italy and sites in NI, i.e. each company will run a similar trial with identical numbers on different sites. The request and the funding to provide 75 devices on each country and aim at performing a validation on maximum 2 patients per device is a clear requirement of the project. We have then defined the primary and secondary outcomes that we consider crucial for evaluating our proposed technology.

The primary outcome will be evaluated in an anonymised form and considered good if planned KPIs are met or exceeded. Secondary outcomes will be evaluated using an unpaired test to compare pre and post intervention measured values, whereas the Chi-square test will be used to detect the significance of outlier proportions, p values smaller than 0.05 will be considered statistically significant. All calculations will be performed using the Matlab software tool (The Mathworks Inc., Natick, MA, USA). We are also interested in evaluating possible correlations among results for the different groups of patients under examination (male and female <55 years old, 55-70, more than 70) to be better prepared for a future clinical investigation of our device.

All details related to the Data Management are provided in Annex A - Technical Data Management of the present document.

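### The KPIs of 50 enrolled and 40 active are counts under open recruitment, so they cannot show acceptance: the active share needed for 40 falls from 80% at 50 enrolled to 53% at 75

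*Combined protocol and SAP*

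**What the plan says.** Study goals and objectives states that the "number of enrolled patients at the end of the trial period will be evaluated in order to understand the degree of acceptance", with a minimum target of 50. Under Primary Outcome Measures the enrolment KPI is again 50, followed by "Total number of active patients -> KPI: minimum 40 active patients". An active patient has at least 4 active weeks. The third outcome, "Total number of patients who drop off, meaning that started the study and had less than 4 active weeks", has no KPI. The average number of active weeks is the total "divided by the number of patients enrolled -> KPI: 8 weeks (excluding drop off before 4 weeks").

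On size, Study Design says: "In this pilot study investigators will recruit as many patients as possible as defined within the inclusion and exclusion criteria". It adds: "There will be 75 devices available at the site from September 2018 to December 2019". Each device may be used twice, and Data Management and Statistical Analysis confirms that the "aim at performing a validation on maximum 2 patients per device is a clear requirement of the project". No planned enrolment and no stopping point at 50 is given.

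Data Management and Statistical Analysis describes the aim as finding how many eligible patients are willing to use the technology and for how long. It judges the primary outcome good when the KPIs are reached and rules out statistical analysis of the primary outcomes. Study Design also sets up a screening log of patients approached, with reasons for ineligibility or refusal where given. No outcome or KPI uses that log as a denominator.

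**The concern.** Counts are ordinary recruitment targets for a pilot. The difficulty is that this plan reads them as evidence of acceptance and bases its success rule on them.

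The number enrolled reflects how many patients were approached and for how long, as well as how willing they were. It says nothing about the share who refused. The number active reflects how many were enrolled as well as how many kept using the device. With a fixed threshold of 40 and no fixed enrolment, the rate needed to pass falls as enrolment rises.

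Two sites with the same device performance could therefore report opposite results on the active KPI, and two with very different uptake could report the same result on the enrolment KPI. A reader told only that the KPIs were met could draw the wrong conclusion on the study's main question.

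**Working it through.** **Inputs from the plan.** Enrolment KPI 50; active KPI 40; average active weeks KPI 8; 75 devices; at most 2 patients per device. One patient per device gives N = 75. Device capacity is 75 × 2 = 150, which is a ceiling and not a planned enrolment. The plan gives no rate or derivation behind 50 or 40, so there is no figure of its own to reproduce. True active rates and numbers approached below are assumptions.

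**1. Active share implied by exactly 40 active.** Share = 40/N, with Clopper-Pearson 95% limits.

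| Enrolled N | 40/N | Exact 95% CI |
|---|---|---|
| 50 | 80% | 66 to 90% |
| 60 | 67% | 53 to 78% |
| 75 | 53% | 41 to 65% |
| 100 | 40% | 30 to 50% |
| 150 | 27% | 20 to 34% |

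The shares need no assumption about the true rate.

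**2. Chance of meeting the 40-active KPI.** P(X ≥ 40), X ~ Binomial(N, p), for assumed p. This is for that KPI alone, not for the whole study being called good.

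| Assumed p | N = 50 | N = 60 | N = 75 |
|---|---|---|---|
| 40% | about 0 | about 0 | 1.3% |
| 50% | under 0.1% | 0.7% | 32% |
| 60% | 0.2% | 18% | 90% |
| 70% | 7.9% | 76% | over 99% |
| 80% | 58% | over 99% | over 99% |
| 90% | 99% | over 99% | over 99% |

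From 50% to 80% the result depends heavily on N. At 40% and 90% it hardly does.

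**3. Enrolment KPI.** For illustrative numbers of eligible patients approached: 50/60 = 83% (exact 95% CI 72 to 92%), 50/100 = 50% (40 to 60%), 50/200 = 25% (19 to 32%). The KPI is met in all three.

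**4. Does the 8-week average restore a constraint?** Its wording supports two denominators.

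- Drop-offs excluded: the average does not depend on how many enrolled patients were inactive, so it gives no offset.
- Divided by all enrolled: let active patients average A active weeks and non-active patients w (0 to 3 by definition). The active share needed is a = (8 − w)/(A − w), and exactly 40 active can pass only if N ≤ 40(A − w)/(8 − w).

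The largest possible A is the usage limit, and the plan gives two. Project summary says "Patients will use WeReha for their home rehabilitation in addition to traditional treatments for up to 12 weeks", and Safety Considerations also gives 12 weeks. Study goals and objectives and several later sections give 20.

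- A = 12: a = 8/12 = 67% (w = 0) or 5/9 = 56% (w = 3); N ≤ 40 × 12/8 = 60 or 40 × 9/5 = 72.
- A = 20: N ≤ 40 × 20/8 = 100 or 40 × 17/5 = 136.
- At a = 0.5, A = (8 − 0.5w)/0.5, which is 16 (w = 0) or 13 (w = 3). A pass with a minority active therefore needs A above 16 or above 13, which is impossible under a 12-week limit and possible under 20.

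**5. Does the activity KPI help?** It asks for 45 minutes a week, measured in active weeks only. An active week already requires 3 sessions of 15 minutes, 3 × 15 = 45, so this KPI adds no constraint on the active share.

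**The case against.** The strongest reply is that acceptance does not rest on these counts alone. Active weeks, exercise time and a 22-item Technology Acceptance Model questionnaire are also primary outcomes. Enrolled, active and drop-off counts will all be reported, so anyone can divide one by another, and the log already holds the patients approached. The study calls itself a pilot, its device numbers are set by the funder, and leaving the primary outcomes without statistical analysis is a stated choice. Any single pass probability also rests on an assumed active rate.

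Part of this stands. The data will exist, the gap is in what is pre-specified, and the size of the swing depends on the rate, which is why a range is shown. But the questionnaire has no KPI and goes only to participants, so it cannot speak for those who refused. The success rule uses the KPIs and not the derivable proportions. The change in 40/N needs no assumed rate, and the fall to 53% occurs at one patient per device, without any reuse.

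The proposed uptake proportion has its own limit. Ward staff pre-screen and highlight patients before approach, so it depends partly on their selection, and it mixes willingness to join a study with acceptance of the device. It is still more informative than a count without a denominator.

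**Conclusion.** The concern holds and should be acted on. The enrolled count cannot show the degree of acceptance, and the 40-active KPI corresponds to an active share of 80% at 50 enrolled, 53% at 75 and 27% at device capacity. At an assumed true active rate of 60%, the chance of meeting that KPI moves from 0.2% to 90% between 50 and 75 enrolled. The swing is also large at 50%, 70% and 80%, and small at 40% and 90%. Whether the 8-week average limits this cannot be settled from the text, because its denominator is worded two ways and the usage limit is given as both 12 and 20 weeks. The shares follow from the plan's own numbers. The pass probabilities and uptake figures rest on assumed rates and assumed numbers approached.

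**What to change.** - Pre-specify two primary descriptive outcomes, each with an exact 95% CI: (a) consented / eligible patients approached, from the screening log; (b) active / all enrolled.
- For (a), enter community patients identified through the Trust investigator in the same log, report volunteers separately, and note that staff pre-screening precedes approach.
- Keep 50 as a recruitment target only, and remove the statement that it shows the degree of acceptance.
- State one denominator for the 8-week average.
- Reconcile the 12-week and 20-week passages, since the meaning of that average depends on them.
- Replace the statement that the primary outcomes will have no statistical analysis with descriptive estimates and 95% CIs.
- Whether to restate the active KPI as a proportion, and at what level, is the sponsor's choice.

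The cost is a few lines of text and minor log coding: a flag for route (ward, community, volunteer) and an eligible/ineligible code for patients who give no reason. The counts for (b) are already primary outcomes. No extra patients or visits are needed. The downside for the sponsor is that a proportion may look less favourable than the count.
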